Determining the neurophysiological relationship between repeated uterine inflammation, dysmenorrhea, and COS, and how OCs might reverse that influence, could define a new pathway for understanding the etiology of CPP/PBS. Secondly, identifying early markers of risk could ultimately underlie an effective prevention strategy because the onset of PBS is often gradual with limited symptoms.³²

B. Research Design and Methods

B.1. Overview:

Diagram 2: After screening and washout, dysmenorrhea sufferers with and without COS, PBS patients, and chronic pain participants (with and without pelvic pain conditions) will be compared with controls on experimental pain sensitivity tests (**PPT**), which measure descending inhibition (**CPM**) and pelvic and bladder sensitivity (**Phase #1**). Women with dysmenorrhea with COS and PBS will be asked to participate in Phase #2. In Phase #2, a trial of cyclic and continuous OCs

will be used to differentiate the individual contributions of circulating sex hormones and repeated sensitizing events (painful menstrual periods) on descending and peripheral mechanisms of bladder pain. All participants will also complete a yearly follow-up questionnaire for 5 years (for participants who complete phase 2, the year 1 questionnaire will be incorporated into the 12-month testing Assessment #3 testing session).

This study will enroll a total of approximately 1,080 participants (See **Appendix 1**). Of those subjects, all will be enrolled at NorthShore University HealthSystem (NorthShore). This leaves a total of approximately 1,080 participants to be enrolled in arm #1 (1,020) and arm #2 (60) of the study. We anticipate that some arm 1 and arm 2 participants (up to 415 arm 1 and 10 arm 2 participants) may become ineligible after the screen visit and/or daily diary data because their pain levels do not clearly place them into a defined group, they are enrolled as a dysmenorrhea participant but do not show evidence of COS, medical reasons are identified at the screen visit that were not identified during the phone screen, or they become lost to follow-up between the screen and assessment visit. We expect approximately 645 arm 1 and arm 2 participants will continue the study and complete Phase 1; 515 will be women with dysmenorrhea, 40 will be women with PBS, 40 will be healthy women without pelvic pain or painful periods, 7 will be “special” healthy controls, and 43 will be women with chronic pain.

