collected electronically using REDCap at home. If requested, paper versions can be provided instead and mailed in. For participants continuing to Phase 2, the year 1 annual medical history questionnaire will usually take place during their assessment #3 visit. All participants that complete phase 1 (Screen + Assessment #1), including phase 2 dropouts, will be asked to complete the annual follow-up questionnaire.

Group (Sample Size)	H (20)	D (20)	D+COS (95)	PBS (40)	P (50)	MSA
Bladder Pain at FU (VAS)	0	0	2.5	3.0	-	0.85
Pelvic Hyperalgesia (VAS)	0	0	3	3	-	0.84
Pelvic Hyperalgesia (Time)	0	0	2	2.5	-	0.83
Pelvic Pain Thresholds	0	.5	.5	2.3	-	0.81
Bodily Pain Thresholds	0	1.5	2	2	2.3	0.91
Conditioned Pain Modulation	0	1-2	1-2	4 _a	2-4 _b	0.94
Menstrual Pain History	0	3.7	5	6	-	0.81
Temporal Summation	0	0	.7	.8	-	-
Estradiol	0	1-3 _c	1-3 _c	1-3	-	0.84
Depression/Anxiety	0	.3	.4	2	2-4	0.82

Table X: Sample sizes and hypothesized results in Z-scores or range of Z-scores (relative to healthy) for subjects that are healthy (H), have dysmenorrhea (D), have cross organ sensitization (D+COS), PBS, or chronic pain (P). MSA indicates Kaiser's measure of sampling adequacy. Numbers in italics indicated minimum detectable hypothesized score with current sample size. Z-scores based on preliminary data, or others indicated by subscript (a: ⁹, b: ^{11,13}). Effects temporal summation in these populations are unknown, but effect sizes as large as 1.1 have been reported for fibromyalgia. Dashes (-) indicate unknown effect size.

C1.h Data Analysis/Sample Size Requirements: The primary outcomes under this hypothesis will be [1] bladder pain at FU, [2] pelvic hyperalgesia (VAS, time to return to baseline pain), reflecting peripheral dysfunction/sensitization, and [3] centrally mediated hyperalgesia (CPM, bodily pain thresholds).

Factor [1], Bladder pain at FU: Our preliminary data on healthy subjects and women with dysmenorrhea, in combination with other studies investigating migraine and PBS, suggests effect sizes between 1.4-5.6 (Cohen's d). As a control comparison, we expect that women with chronic pain will have levels of bladder and pelvic sensitivity comparable to healthy subjects. We will perform t-tests for each of these three pain variables using pairwise contrasts and appropriate Bonferroni corrections for six group comparisons.

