Factor [2], pelvic hyperalgesia: To confirm pelvic hyperalgesia (*but not necessarily pelvic PPT*) is higher in those with bladder pain, we will show bladder pain and pelvic hyperalgesia (both VAS and TIME) are higher in D+COS than healthy pain-free controls (H), dysmenorrhea only (D), and chronic pain patients (P). Similarly bladder pain, pelvic hyperalgesia and pelvic floor pain sensitivity (PPT) are anticipated to be greater in PBS than H, and D.

Factor [3], centrally mediated hyperalgesia: Greater central dysfunction manifest by impaired CPM and reduced bodily pain thresholds in vulnerable subjects will be shown by comparing D+COS, PBS, and P to D and H. We estimate 15 subjects per group will provide adequate power (g-power, a priori t-test, $\alpha=0.05$, $\beta=0.2$). To verify we have adequate phenotyping of CPM, we have included the positive control group with chronic pain (P). We assumed the

[figure not shown]
difference in CPM between healthy subjects and chronic pain patients in this protocol would have an effect size of 0.78 based on a meta-analysis (Lewis et al. 2012). Using a 2.6 allocation ratio, a priori power analysis ($\alpha=0.05$, $\beta=0.2$), suggests we need 20 healthy participants and as many as 50 chronic pain patients to detect a difference in the mean CPM. Additionally, the utilization of 50 chronic pain patients will allow us to use regression to identify up to 5 predicted factors associated CPM with correlation coefficients exceeding 0.3 even after correcting for multiple comparisons ($\alpha=0.05$, $\beta=0.2$) as suggested by an a priori random model power analysis. This will be readily captured as our global study design encompasses a larger sample size (Table X) to handle anticipated secondary analysis and projected needs for completion of Phase #2.

Additional confirmatory analysis: Special healthy control subjects (n=10), we will verify special healthy control subjects do not differ from original enrolled healthy control subjects (n=20) to ascertain chronic subjects (P) participating in the trial are not treated differently under blinded conditions.

For the secondary analysis of Phase #1, we will evaluate the D+COS (provoked bladder pain) phenotype while accounting for menstrual history (including historical OC exposure), hormonal factors, anxiety, and depression. To determine the relative contribution of these secondary variables on bladder pain, we will perform principal component analysis (PCA).

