We have adequately powered the analysis of these potential covariates consistent with a bootstrap (n=1000 replications, Fig Y) model based on our preliminary data and studies by others (described in Table X). Even with weak correlations ($r=.3$), PCA can detect 3 primary factors with our projected sample size. PCA is an optimal method to identify the mechanisms responsible for bladder pain. Historically PCA with even smaller sample sizes has been employed to measure how coping skills influence pain perception during the menstrual cycle⁵² (n=20) and to show that different pain testing modalities are related to differential psychosocial profiles⁵³ (n=188). Even if PCA fails, we can make many direct comparisons beyond what is described here with t-tests.

Fig Y: Bootstrap simulation constructed assuming a range of correlations between potential mechanisms (e.g. pelvic hyperalgesia and bladder pain) indicate that even with weak correlations we can detect 3 factors. Error bars show 95% confidence intervals.

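### Fifty chronic pain patients do not give 80% power to identify CPM factors correlated at 0.3 after multiplicity correction: under two-sided Bonferroni over five, power is about 33% per factor and the detectable correlation is about 0.46

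*Combined protocol and SAP*

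**What the plan says.** In section C1.h, under Factor [3], the plan first sizes the CPM comparison of chronic pain patients with healthy women, then adds a second use for the same patients. It states that this group is large enough to "identify up to 5 predicted factors associated CPM with correlation coefficients exceeding 0.3 even after correcting for multiple comparisons". It gives alpha 0.05 and beta 0.2, and describes the basis as follows: "as suggested by an a priori random model power analysis". The claim is tied to the chronic pain group by name: "the utilization of 50 chronic pain patients will allow us to use regression".

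The plan does not say:
- which multiplicity correction applies to this regression (Bonferroni is named under Factor [1], but for the group contrasts: "appropriate Bonferroni corrections for six group comparisons");
- whether the tests are one- or two-sided;
- whether 0.3 is a simple, partial or multiple correlation.

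The next sentence adds that the global design has a larger sample, citing Table X. Section B.1 expects fewer than 50 chronic pain patients to finish Phase 1: "43 will be women with chronic pain".

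**The concern.** A correlation of 0.3 explains 9% of the variance, and 50 patients is a small sample for detecting that even in a single test. A claim of 80% power for up to five such factors after correction therefore looked too favourable.

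What is at stake is how a negative result is read. If the printed 80% is believed, a factor not found in the chronic pain group will be taken as unrelated to CPM. If power is nearer one in three, that conclusion is unsupported. The regression is an additional analysis and none of the primary group contrasts depends on it, so the damage is to interpretation and not to the main design.

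**Working it through.** **Inputs.** From C1.h: n = 50, r = 0.3, up to five factors, alpha 0.05, power 0.80. From B.1: 43 chronic pain completers. Assumed, because not printed: two-sided tests with Bonferroni over five, so alpha = 0.05/5 = 0.01 per factor. Other choices are shown below.

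**The neighbouring calculation.** The CPM contrast in the same paragraph (d = 0.78, 20 versus 50, two-sided 0.05) reproduces, with power 0.83. The problem is confined to the regression sentence.

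**Power for one correlation of 0.3 (Fisher z).** Power ≈ Φ(atanh(r)·√(n−3) − z).
- atanh(0.3) = 0.3095 and √47 = 6.856, so the product is 2.122.
- Two-sided 0.01, n = 50: Φ(2.122 − 2.576) = Φ(−0.454) = 0.325.
- Two-sided 0.01, n = 43: √40 = 6.325, so Φ(1.958 − 2.576) = Φ(−0.618) = 0.268.

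**Exact power under the random (bivariate-normal) model, r = 0.3:**

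| Alpha per factor | n = 50 | n = 43 |
|---|---|---|
| 0.01 two-sided | 0.33 | 0.27 |
| 0.01 one-sided | 0.42 | 0.36 |
| 0.05 two-sided (no correction) | 0.57 | 0.51 |
| 0.05 one-sided (no correction) | 0.69 | 0.63 |

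No cell reaches 0.80, including those with no correction.

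**Detectable correlation at 80% power, two-sided 0.01.** r = tanh[(2.576 + 0.842)/√(n−3)]. For n = 50, tanh(3.417/6.856) = tanh(0.498) = 0.461. The exact method gives 0.458 (n = 50) and 0.490 (n = 43). One-sided 0.01 gives 0.43 and 0.46.

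**Sample size for r = 0.3.** n = (3.417/0.3095)² + 3 = 121.9 + 3, so 125 at two-sided 0.01. One-sided 0.01 needs 107 (exact method).

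**All five factors in one regression.** If all five are real, each has r = 0.3 and they are mutually uncorrelated, R² = 5 × 0.09 = 0.45. The partial correlation of each is 0.3/√(1 − 0.45 + 0.09) = 0.375, which is the most favourable setting for per-factor tests. Simulated power per real factor (20,000 replicates, n = 50):

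| Real factors | Two-sided Bonferroni | Two-sided Holm | Two-sided Benjamini-Hochberg | One-sided Benjamini-Hochberg |
|---|---|---|---|---|
| 5, uncorrelated | 0.51 | 0.61 | 0.70 | 0.81 |
| 4, uncorrelated | not run | 0.49 | 0.58 | 0.71 |
| 3, uncorrelated | 0.37 | 0.40 | 0.47 | 0.60 |
| 1, uncorrelated | 0.29 | 0.29 | 0.30 | 0.39 |
| 5, correlated 0.1 | 0.18 | not run | not run | 0.39 |

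One cell reaches 0.80. With 43 completers it is 0.73. Even at n = 50, all five factors are found together in only about 42% of replicates. The plan's own simulation does not assume uncorrelated mechanisms; the Fig Y caption reads "Bootstrap simulation constructed assuming a range of correlations between potential mechanisms".

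**Other readings of 0.3.** An omnibus random-model F test with five predictors and R² = 0.3 has power 0.92 (alpha 0.05) or 0.77 (alpha 0.01) at n = 50. If 0.3 is the multiple correlation, so R² = 0.09, power is 0.31 or 0.13. Pooling all Table X groups (20 + 20 + 95 + 40 + 50 = 225) gives Φ(0.3095 × √222 − 2.576) = Φ(2.036) = 0.98 for r = 0.3 at two-sided 0.01.

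**The case against.** The strongest defence is that the sentence never says power is per factor, and that 33% and 0.46 are simple-correlation figures while the plan says regression. If up to five factors means at least one of five, beta = 0.2 can be met. With five real, uncorrelated factors and two-sided Bonferroni at n = 50, the chance of finding at least one is 0.88 (simple correlations) or 0.96 (five-predictor regression). The term random model also belongs to regression power software, so 0.3 may be an R-squared reported as a correlation; at alpha 0.01 that gives 0.77, close to 0.80. Finally, the next sentence cites the larger Table X sample, where power is ample.

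Part of this stands. The 33% does rest on an assumed correction and a simple correlation, and under the most favourable regression model two-sided Bonferroni gives 51% per factor. The R-squared explanation is plausible, but it is inference.

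None of it supports the sentence as written. Finding at least one factor is not identifying up to five: all five are found in 5% of replicates or fewer in the two settings behind the 0.88 and 0.96. The at-least-one figure also drops to 0.70–0.74 with three real factors and to about 0.3 with one. An omnibus test identifies no individual factor, and an R-squared of 0.3 is not a correlation of 0.3. The power claim is attributed to the 50 chronic pain patients, not to the pooled sample.

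**Conclusion.** The power statement is wrong as written. Under two-sided Bonferroni over five factors, 50 chronic pain patients give about 33% power per factor for a simple correlation of 0.3 (27% with 43), and the detectable correlation is about 0.46 (0.49 with 43). On that reading a real factor at 0.3 is missed about two times in three.

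The exact percentage depends on the unprinted correction and sidedness, but the failure does not: a simple correlation of 0.3 falls short of 80% even uncorrected. The single per-factor reading found to reach 80% needs one-sided testing, false-discovery-rate control, 50 completers and five real, uncorrelated factors together. The point should be corrected, but it does not threaten the primary contrasts.

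**What to change.** In C1.h, Factor [3], replace the correlation of 0.3 with the value the sample can detect: about 0.46 for 50 patients or 0.49 for 43, at two-sided alpha 0.01 per factor. Name the correction and the sidedness, and say whether the coefficient is simple or partial and whether power is per factor.

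Two alternatives are acceptable if they reflect what was intended:
- If the regression pools the Table X groups, say so, give the pooled n, and stop attributing the power to 50 chronic pain patients.
- If the calculation was an omnibus R-squared test, print the R-squared and drop the claim that individual factors are identified.

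This is a text change with no extra patients or procedures. The cost is a less favourable detectable effect, unless pooling is declared.

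A minor reconciliation can be made in the same edit. The CPM contrast, where the plan "suggests we need 20 healthy participants and as many as 50 chronic pain patients to detect a difference in the mean CPM", is correct at alpha 0.05. The plan should say whether the six-comparison Bonferroni of Factor [1] also covers it, and reconcile the 20 healthy women here with the 40 in B.1. At 0.05/6, power is 0.59 with 20 versus 50 and about 0.80 with 40 versus 43.

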Controls: 1) **Healthy control cases** will have a) average pain \leq 3/10 with menses or with withdrawal uterine bleeding from cyclical OCs and b) no concurrent chronic pain diagnoses or \geq 5 migraines in the past year. Healthy controls with < 2 migraines per year will be recruiting preferentially.

Exclusion criteria for dysmenorrhea (and D+COS), PBS and healthy control cases includes: a) presence of active pelvic or abdominal malignancies (primary or metastatic), b) absence of regular menses (including current pregnancy, recent pregnancy, or active breast feeding) c) active genitourinary infection in the last four weeks, d) unable to read or comprehend the informed consent in English, e) unwilling to complete study procedures f) presence of hypertension or risk for developing hypertension, and g) unwilling to withdraw from OCs for at least one cycle prior to the Phase #1 study visit. Participants with a history of epilepsy will not complete the visual unpleasantness task.

Inclusion/Exclusion Criteria for “Special” Healthy Controls and Chronic Pain Participants (Arm 2)

Special Healthy Controls (n=10) will be enrolled under the same inclusion and exclusion criteria as healthy controls, however, special healthy controls will not be required to have regular periods or abstain from hormonal contraception, and will not be assessed for migraines with aura.

Chronic pain cases (n=50) will have a diagnosed, documented (reviewed by PI) chronic pain disorder greater than six months' duration, which has required at least 2 different prescription treatments and/or surgical management. They must report an average pain of at least 5/10 in the last month. We will accept participants with any type of chronic pain (except for individuals with bilateral knee and hand pain) but anticipate many of our chronic pain participants to suffer from fibromyalgia, lower back pain, and chronic pelvic pain (including irritable bowel syndrome).

Of note, special healthy controls or chronic pain cases will not be excluded for unwillingness to undergo internal PPT testing, visual sensory testing, hip or head PPT. These groups may waive these procedures but still remain eligible to choose to participate in rest of the study.

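### With 10 special healthy controls against 20 healthy controls and no margin, the Phase 1 check cannot verify that the two groups do not differ

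*Combined protocol and SAP*

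**What the plan says.** The check is in section C1.h of the combined protocol and SAP, under the paragraph that begins "Additional confirmatory analysis: Special healthy control subjects (n=10". It reads: "we will verify special healthy control subjects do not differ from original enrolled healthy control subjects (n=20". Its stated purpose is to show that chronic pain participants were not handled differently by blinded testers. The paragraph names no outcome, test, significance level, margin, confidence interval or rule for passing. Earlier in C1.h, the test named for comparing Phase 1 groups is the t-test, with a Bonferroni correction for six comparisons.

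Two other places bear on the check:

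- Section B.1 gives different expected numbers completing Phase 1: "40 will be healthy women without pelvic pain or painful periods" and "7 will be “special” healthy controls".
- The Arm 2 eligibility section says that "special healthy controls will not be required to have regular periods or abstain from hormonal contraception". Arm 1 healthy controls must have regular menses and be willing to stop oral contraceptives before the Phase 1 visit.

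**The concern.** The paragraph sets out to reach a conclusion of no difference, and then to draw a second conclusion from it about how P participants were handled. A comparison of two small groups supports the first conclusion only if it could have revealed a difference worth worrying about, or if the confidence interval is narrow enough to rule one out. The plan shows neither.

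The P group is the positive control for CPM: section C1.j relies on it to decide whether a null CPM finding is a true negative. If P participants were tested differently, part of the P versus healthy difference could be an artefact. A statement that this had been checked and excluded would reassure readers more than 10 against 20 women can justify.

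The second difficulty is interpretation. The two control groups may differ in hormonal contraceptive use and cycle status. Section C1.f treats reproductive hormones as a possible influence on pain sensitivity. Section C1.e schedules Arm 2 women who lack regular periods or use hormonal contraception outside the luteal-phase rule. A difference between the groups could therefore be hormonal, and a hormonal effect could also hide a difference caused by testing.

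**Working it through.** **Inputs.** Group sizes of 10 and 20 (C1.h); 7 and 40 as the alternative (B.1). The effect of 0.78 SD is the plan's value for CPM in P versus healthy women (C1.h). Alpha of 0.05 is stated in C1.h for that calculation, not for this check. The 0.5 SD effect is an assumption. Two-sided testing is also assumed.

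**The plan's nearest figure.** C1.h gives no power for the check itself. It does size P versus healthy: d = 0.78, alpha 0.05, power 80%, ratio 2.6, giving 20 healthy and up to 50 P. An exact two-sided t-test calculation gives 19 + 50 (power 81.4%), and 20 + 50 has power 82.8%. A one-sided test would need only about 15 + 39. So the plan's figure reproduces as a two-sided t-test, and the same method is applied to the check.

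**Power of the check.** The noncentrality is d / √(1/n₁ + 1/n₂), with n₁ + n₂ − 2 degrees of freedom.

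- 10 v 20: √(1/10 + 1/20) = 0.387, df = 28, critical t = 2.048. At d = 0.5 the noncentrality is 0.5/0.387 = 1.29. At d = 0.78 it is 2.01.
- 7 v 40: √(1/7 + 1/40) = 0.410, df = 45, critical t = 2.014.

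| True difference (SD) | Power, 10 v 20 | Power, 7 v 40 |
|---|---|---|
| 0.5 (assumed) | 24% | 22% |
| 0.78 (plan's CPM effect) | 49% | 46% |
| 1.0 | 70% | 67% |
| 1.5 | 96% | 95% |
| 2.0 | 99.9% | 99.8% |
| Difference giving 80% power | 1.12 | 1.17 |

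**Sensitivity, 10 v 20.** One-sided testing gives 35% at 0.5 and 63% at 0.78. With the six-comparison Bonferroni correction, two-sided power is 8% and 23%.

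**Precision.** The 95% CI half-width is critical t × √(1/n₁ + 1/n₂), in SD units:

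- 10 v 20: 2.048 × 0.387 = 0.79 SD
- 7 v 40: 2.014 × 0.410 = 0.83 SD

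Both are about the size of the 0.78 SD effect. The largest difference that a result leaves open is the absolute observed difference plus the half-width. Simulating a true difference of zero, the median of that bound is about 1.06 SD for 10 v 20. The whole interval falls within ±0.8 SD only about 10% of the time (about 5% for 7 v 40).

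**As a formal equivalence test.** With two one-sided 5% tests, a true difference of zero and 10 v 20, power is 0.2% for a 0.5 SD margin, 26% for 0.78 SD, 62% for 1.0 SD and 83% for 1.2 SD. These margins are illustrative, since the documents give none.

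**The case against.** Several points on the other side are fair.

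*The criterion is not stated.* C1.h does not say that a non-significant t-test counts as a pass, and the check is not named among the six comparisons. That stands: the t-test reading is an inference. But no other criterion is written down, and the confidence interval and equivalence figures reach the same conclusion without it.

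*The check is not empty.* A reader might infer that it would pass almost whatever the truth. The figures do not support that. The 24% depends on an assumed 0.5 SD; at the plan's 0.78 SD a difference would be detected about half the time, and at 1.5 SD 96% of the time. Table X hypothesises P versus healthy differences of 2.3 SD for bodily thresholds and 2 to 4 SD for CPM. An artefact of that size would almost always be found. The weakness concerns small and moderate differences.

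*Nothing formally depends on it.* A reader might infer that every P contrast rests on this check, or that it is the only safeguard. The documents do not say so. It is labelled additional, and no P contrast is conditional on it. Standard ramp rates and cut-offs, a trained clinician for the pressure tests and automatic saving of threshold values also support like-for-like testing.

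*Hormonal differences are allowed, not imposed.* A reader might take the two groups to differ by design. The Arm 2 criteria only waive requirements, and C1.f measures E2, P4 and testosterone in both arms. That limits the point to possible confounding, which can be described.

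**Conclusion.** The concern holds as a limited point about a secondary quality check. With 10 v 20 women, a non-significant result could not verify that the control groups are alike, and so could not show that P participants were handled alike. Under a two-sided 5% t-test on one measure, power is 24% at an assumed 0.5 SD and 49% at 0.78 SD, and 80% is reached only at about 1.1 SD. With 7 v 40 the figures are 22%, 46% and 1.17 SD. Possible differences in contraceptive use and cycle status mean that neither result can be attributed to tester behaviour alone.

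This rests on the t-test reading and on the stated or expected group sizes. Special healthy controls may waive internal pressure testing, so numbers for the pelvic measures could be smaller. No primary contrast changes. A reader might also infer that the check rules out anything above about 0.8 SD. It does so only if the observed difference is exactly zero.

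**What to change.** In C1.h, replace the undertaking to verify no difference with the following:

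1. Report the estimated difference between special healthy controls and healthy controls, with its 95% CI, for each Phase 1 primary measure. State which healthy controls are compared (C1.h has 20, B.1 expects 40) and the number contributing to each measure.
2. Report hormonal contraceptive use in each group beside these estimates.
3. State that the expected half-width is about 0.8 SD, so differences as large as the 0.78 SD used to size P versus healthy CPM generally cannot be excluded.
4. Call the check descriptive. Claim equivalence only if the interval lies within a margin stated in advance.

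This costs a few lines of SAP text and needs no extra participants or procedures. The plan gives up a claim of verification that its numbers could not support. Formal equivalence would be a different undertaking: at 80% power, a true difference of zero and 1:2 allocation, the normal approximation gives about 22 special and 43 healthy controls for a 0.78 SD margin, or 52 and 103 for 0.5 SD.

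### PCA on its own cannot give the adjusted, ranked contributions to bladder pain that the Phase 1 secondary analysis is meant to deliver

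*Combined protocol and SAP*

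**What the plan says.** The secondary analysis in C1.h is to evaluate the D+COS phenotype, identified with provoked bladder pain, "while accounting for menstrual history (including historical OC exposure), hormonal factors, anxiety, and depression". The method follows at once: "To determine the relative contribution of these secondary variables on bladder pain, we will perform principal component analysis (PCA"). The protocol justifies the choice by stating that "PCA is an optimal method to identify the mechanisms responsible for bladder pain".

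The sample-size support is "We have adequately powered the analysis of these potential covariates consistent with a bootstrap (n=1000 replications, Fig Y) model", from which the plan concludes that even at r = 0.3 "PCA can detect 3 primary factors with our projected sample size". The Fig Y legend describes a simulation "assuming a range of correlations between potential mechanisms (e.g. pelvic hyperalgesia and bladder pain"). Table X gives each measure except temporal summation a value in its last column, where "MSA indicates Kaiser's measure of sampling adequacy". Bladder pain at first urge has the value 0.85.

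The fallback is "Even if PCA fails, we can make many direct comparisons beyond what is described here with t-tests". C1.j adds cluster analysis if the Phase 1 comparisons are nonsignificant. The only regression named for Phase 1 (C1.h, Factor [3]) has CPM as its outcome and is justified by the 50 chronic pain patients.

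C1.i expects central factors to account for most of the variability in bladder pain sensitivity. It also looks to the results for the importance of systemic E2 relative to modifiable factors such as menstrual pain.

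**The concern.** The question concerns one outcome: how much each of several correlated variables contributes to bladder pain once the others are taken into account. PCA answers a different question. It finds the combinations of the entered variables that carry most of their joint variance, and it treats every entered variable alike. A large loading means that a variable moves with the others in that component. It does not show that the variable predicts bladder pain when the rest are held fixed.

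At stake is the separation of mechanisms. Section A faults earlier work for leaving out E2 and psychological factors and undertakes to adjust for them. If the Phase 1 answer is read from loadings, a covariate that is merely correlated with the true driver can look as important as the driver. The hormonal, menstrual and psychological explanations would then not be told apart.

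**Working it through.** **1. The plan's own figure.** Three factors at r = 0.3 cannot be strictly reproduced: the block structure, the number of variables, the retention rule and Fig Y are not available. The check assumed three blocks, 9 or 10 variables, within-block r = 0.3 and 1000 replications. The sample sizes come from Table X: 95 (D+COS), 20 + 20 + 95 + 40 = 175 (without chronic pain), and 175 + 50 = 225.

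| Between-block r | Rule | n = 95 | n = 175 | n = 225 |
|---|---|---|---|---|
| 0 | parallel analysis, exactly 3 | 77–82% | 99% | over 99% |
| 0.1 | parallel analysis, exactly 3 | 26–31% | 56–63% | 70–80% |
| 0 or 0.1 | eigenvalue > 1, at least 3 | 98–100% | over 99% | over 99% |

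The claim is plausible under favourable assumptions. It concerns how many components can be found, not how much any variable contributes to bladder pain.

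**2. Aim against method.** Each planned Phase 1 step, set against what the aim requires:

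| Step | Bladder pain as outcome? | Adjusts for covariates? |
|---|---|---|
| PCA (C1.h) | no | no |
| t-tests as fallback (C1.h) | possible | no |
| cluster analysis (C1.j) | no | no |
| regression (C1.h, Factor [3]) | no, CPM | not for bladder pain |

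In Phase 2 (C2.h), Z1 adjusts for E2 and P4, and Z5 compares women with more and less than 50% improvement. Both address change during the trial and leave the Phase 1 question open.

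**3. An example with a known answer.** Assumed: five standardised covariates (menstrual history, E2, P4, anxiety, depression), all pairwise r = 0.3 except anxiety–depression 0.6. Bladder pain = 0.6 × menstrual history + noise, with total variance 1. Then R² = 0.6² = 0.36. Its correlation with bladder pain is 0.6 for menstrual history and 0.6 × 0.3 = 0.18 for each other covariate. The regression shares are a Shapley split: each predictor's gain in R², averaged over all orders of entry.

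| | Menstrual | E2 | P4 | Anxiety | Depression | Bladder pain |
|---|---|---|---|---|---|---|
| PC1, covariates only | 0.62 | 0.62 | 0.62 | 0.76 | 0.76 | not entered |
| PC1, bladder pain entered | 0.72 | 0.59 | 0.59 | 0.71 | 0.71 | 0.58 |
| PC2, bladder pain entered | 0.51 | −0.14 | −0.14 | −0.43 | −0.43 | 0.69 |
| Shapley share of R² | 0.32 | 0.01 | 0.01 | 0.01 | 0.01 | – |

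- With bladder pain left out, the first row is the same whether the only cause is menstrual history, E2 or anxiety, or there is none. The regression separates these cases: 0.32 of 0.36 goes to menstrual history, 0.32 to E2, or 0.28 to anxiety, and R² is 0 in the last.
- With bladder pain entered, PC1 puts anxiety and depression level with the true cause. PC2 (eigenvalue 1.15) does pair bladder pain with menstrual history.
- The share of bladder pain's variance on the two components is 0.58² + 0.69² = 0.34 + 0.48 = 0.82, against a true explained share of 0.36. Bladder pain helps to form the components, so this share is not variance explained by the covariates.

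**4. Is an outcome model feasible?** Test of one coefficient among five at two-sided α = 0.05: f² = partial R²/(1 − partial R²), noncentrality n × f², F on 1 and n − 6 degrees of freedom.

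| n | Partial R² 0.04 | Partial R² 0.09 |
|---|---|---|
| 95 | 50% | 86% |
| 175 | 77% | 98% |
| 225 | 86% | over 99% |

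For example, n = 95 and 0.09 gives 95 × 0.09/0.91 = 9.4 and 86% power. Table X's two dysmenorrhea groups (20 + 95 = 115) fall between the first two rows. The 225 is an upper figure for any model with pelvic thresholds, because chronic pain participants may waive internal testing.

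**The case against.** The best defence is that bladder pain is probably entered. It has its own sampling-adequacy value in Table X, and the Fig Y legend uses it in an example pair. PCA then shows which variables travel with bladder pain. If three components are examined, as the plan intends, PC2 in the example points to the right cause. With no true cause, bladder pain loads 0 on PC1 and forms a component of its own. This stands as description, and a reader who infers that PCA says nothing at all about bladder pain goes too far. It does not rescue the stated aim: co-loading is unadjusted, and the variance share it yields (0.82 against 0.36) is not a contribution of the covariates.

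A reader might also take C1.i as a conclusion the plan intends to read off PCA loadings. The text states an expectation, in line with published meta-analyses, and does not say which analysis will establish it. The supportable point is that no Phase 1 analysis written in the plan could establish it.

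Nor do the documents support reading this as a flaw in the main Phase 1 results. The primary pairwise t-tests do not depend on the PCA.

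**Conclusion.** Wrong as written. The plan assigns an adjusted, ranked question about one outcome to a method without an outcome or adjustment, and no later Phase 1 step supplies the missing model. PCA alone can support neither the relative contributions sought in C1.h nor the variance-explained statement anticipated in C1.i.

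The point about method needs no assumptions. The illustrated size does: the correlations, the effect of 0.6 and the block structures are assumed, and other values would give other loadings. The power figures assume five covariates; a longer list of correlated predictors leaves each with a smaller partial R². The defect is confined to a secondary analysis.

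**What to change.** Replace the PCA sentence in C1.h with an outcome model:

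- **Model.** Multivariable regression, or principal component regression, with continuous bladder pain VAS at first urge as outcome. Name its scale, since the D+COS definition in C1.a uses 0–100 and the bladder test in C1.e records 0–10.
- **Predictors.** Those already collected: CPM, bodily and pelvic pain thresholds, menstrual pain and contraceptive history, E2 and P4, anxiety, depression.
- **Population.** State it, for example all dysmenorrhea participants with and without COS. D+COS is defined by bladder pain above 15, so a pooled R-squared depends on the group mix, and one within D+COS alone is restricted in range. State the expected number too: Table X implies 115 such women, while B.1 expects 515 with dysmenorrhea to complete Phase 1.
- **Reporting.** Adjusted coefficients and one prespecified importance measure that handles correlated predictors, such as a Shapley or dominance split of R-squared, with bootstrap confidence intervals.
- **PCA.** Keep it for data reduction or description, and say whether bladder pain is entered.

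The cost is revised wording and a little extra analysis. No new data are needed, and the primary comparisons do not change.
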